They will also be provided a comprehensive exercise safety orientation which is detailed in Appendix 22a. Briefly, the information includes review of devices, supplies, space, safe glucose ranges and carbohydrate snacking for exercise, reminders from CGM training pertinent to exercise, insulin adjustments around exercise, watching for symptoms, and who to call with concerns. They will be provided and instructed to keep carbohydrate-containing foods and drinks (eg, orange juice, glucose tablets) available to use when indicated by glucose testing or symptoms. In addition, they will be educated regarding the American Diabetes Association guidelines for self-monitoring blood glucose and urine ketones, if indicated, and appropriate adjustments of diet and insulin before, during, and after engaging in exercise. For instance, if blood glucose is less than 90 mg/dL, they can consume 10-20g of fast-acting carbohydrates (eg, 4 oz of orange juice or 3 glucose tablets) and wait to commence with exercise until blood glucose is confirmed to be above 90 mg/dL. If blood glucose is greater

Protocol Number 2000035846

August 13, 2024 Version #7

than 270 mg/dL and not associated with a recent meal, they must check their blood for ketones and avoid exercise if they have ketones ≥1.0 mmol/L.

Participants will be encouraged to be vigilant for symptoms of hypoglycemia during exercise and for the remainder of the day because exercise increases the risk for nocturnal hypoglycemia. The symptoms they will be encouraged to be vigilant for include cold, clammy skin, pallor, difficulty concentrating, shakiness, lack of coordination, irritability, hostility, and poor behavior, a staggering gait, fatigue, nervousness, excessive hunger, headache, blurred vision and dizziness, and abdominal pain or nausea. In these instances, they will be advised to refrain from exercise while checking blood glucose.

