All participants participate in routine follow-up, consisting of quarterly visits to the clinic and 24-hour access to nurse and/or physician consultation. It is not anticipated that any of the data collection procedures or the intervention will cause any adverse effects. Nonetheless, the participants will continue to receive routine medical and nursing care throughout the study period, and intervention for adverse effects will be available.

These protocols have been utilized by Drs. [name], [name], and [name] over four prior exercise clinical trials among youth and adults with T1D that had no instances of severe hypoglycemia or diabetic ketoacidosis (HIC #s 1605017843, 2000025992, 2000030105, 2000033736).

**Hyperglycemia:** There is a risk of hyperglycemia due to exercise from factors such as counterregulatory hormone response releasing glucose into the blood.

See above regarding blood glucose testing, blood glucose monitoring review by research staff, Drs. [name], [name], [name], and routine clinical support. Regarding hyperglycemia

August 13, 2024 Version #7

specifically, participants will be encouraged to be vigilant before, during, and after exercise for signs or symptoms of hyperglycemia such as dry mouth, headache, heaviness, pressure behind the eyes, or unusual increase in thirst. They will be advised in these instances to reassess their blood glucose. If blood glucose is greater than 270 mg/dL and not associated with a recent meal, they should check their blood for ketones and avoid exercise if they have ketones ≥1.0 mmol/L.

**Severe hypoglycemia and hyperglycemia:** There is a risk of severe hypoglycemia or hyperglycemia due to exercise.

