Severe hypoglycemia will be defined as any blood glucose level resulting in symptoms which require outside intervention to control (including but not limited to confusion and loss of coordination). Severe hyperglycemia will be defined as blood glucose >500mg/dL, presence of urine ketones or other signs and symptoms of diabetic ketoacidosis (including but not limited to weakness and fatigue, confusion, shortness of breath). Patients will be asked to contact emergency services should these events occur. Specifically, Yale-affiliated patients with T1D have access to a 24-hour hotline with access to nurse and/or physician advice or can choose to call 911. Non-Yale-affiliated patients will be asked to call 911 or contact their providers' after-hours staff (all patients will submit provider information to the study team at study start). The study team will be notified of the event within 24 hours via daily diaries; moreover all participants will have the PI's direct contact information should they choose to contact him earlier by phone or email. Our team will then notify the patient's primary diabetes provider (if not already notified) and all study-related exercise will be suspended until patient receives further advice from their diabetes provider regarding next steps which may include modified exercise routines or suspension of the study altogether. All serious adverse events such as severe hypoglycemia and hyperglycemia will be reported to the PI verbally within 24 hours of study staff being notified and to university's IRB committee in writing within 5 business days. In the case of >1 episode of severe hypoglycemia or 1 episode of diabetic ketoacidosis not closely related to pump site failure, the participant will be removed from the study and referred to their diabetes care provider for follow-up.

**Exercise-related injuries:** Exercise may cause muscle soreness/pain, muscle strain, cardiovascular events, and tiredness during or after the activity.

The probability and magnitude of such injuries varies based upon factors such as the individual participant's fitness level and the difficulty of the exercise routines. Our previous pilot studies (sect. 1.2) had no injuries or muscle strains. The American Heart Association Scientific Statement notes that the frequency of exercise-related out-of-hospital cardiac arrest among the general population ages 35-90yr was measured at 3.0 per 100,000 person-years.

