A, Based on this blood glucose data, it may be a good idea to review the recommendations from your healthcare professional about how you would adjust your food intake or insulin dosing around exercise. If you do not remember, it would be a good idea to reach out. B, If your blood sugar is high (more than 270 mg/dL) before starting exercise, check your blood or urine for ketones. If you test positive for ketones, avoid vigorous activity. If you do not have ketones in your blood or urine and you feel well, it should be fine to exercise.

Tool #4: Health outcome feedback regarding the causal impact of exercise upon blood glucose (Appendix 18). The GlucoseZone cloud will draw CGM metrics (coefficient of variation, mean, % time >180, 70-180, <70mg/dL) and covariates (insulin-on-board, carbohydrates self-reported into insulin device, exercise metrics including video selected and Fitbit minutes / heart rate / distance / calories / sleep / activity at sub-exercise intensity). The app organizes these data on a dashboard accessible to Yale staff. A Yale staff member exports the contents onto the Yale Secure Server weekly and enters them into our Bayesian R-code (Appendix 9b). The EP reviews the results and accompanying visualizations documenting a positive, neutral, or negative effect of exercise once per 1-4 weeks as insights are generated. The EP will message the client by encrypted emailed pdf relaying the most representative results and/or visualizations and any recommended adjustments by interpretating and applying exercise guidelines (e.g., "You have done purely resistance exercise for the past 28 days, and it has had the causal impact of increasing blood glucose time above target range. Consider more aerobic exercise.") If these EP's recommendations indicate repeating certain videos, they will accordingly appear on the home-screen the following week.

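### Table 3 tip B limits only vigorous activity when ketones are positive, whereas section 2.2 tells participants not to exercise at blood ketones of 1.0 mmol/L or more

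*Combined protocol and SAP*

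**What the plan says.** Tool #3 sends each participant a weekly report listing glycemic patterns around exercise, each with a tip. One pattern is starting exercise above 270 mg/dL, and its tip is B. Tip B asks the participant to "check your blood or urine for ketones". It continues "If you test positive for ketones, avoid vigorous activity" and closes with "If you do not have ketones in your blood or urine and you feel well, it should be fine to exercise". It states no ketone cut-off.

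Section 2.2 gives the safety rule twice, for readings above 270 mg/dL not linked to a recent meal. Under Hypoglycemia, "they must check their blood for ketones and avoid exercise if they have ketones ≥1.0 mmol/L". Under Hyperglycemia, "they should check their blood for ketones and avoid exercise if they have ketones ≥1.0 mmol/L".

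Section 2.2 also mentions education on "self-monitoring blood glucose and urine ketones, if indicated", so urine testing has a place in the plan. Its definition of severe hyperglycemia includes "presence of urine ketones or other signs and symptoms of diabetic ketoacidosis", with no minimum level. In that event patients are to contact emergency services, and "all study-related exercise will be suspended until patient receives further advice from their diabetes provider".

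Section 8.7, Tracking A, lists glucose of at least 270 mg/dL with ketones of at least 1.0 mmol/L, during or within one hour of exercise, as diabetic ketoacidosis.

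**The concern.** A participant can receive two different instructions for the same reading. The looser one is targeted: it goes to people who have already started at least one session above 270 mg/dL. Because the report looks back over the week, the tip can affect only later sessions, but shaping later sessions is its purpose.

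Take a later reading of 290 mg/dL with blood ketones of 1.5 mmol/L and no recent meal. Section 2.2 says not to exercise. A participant relying on tip B could take it to leave a gentle session open, and the video library includes flexibility, balance and chair-based routines. One episode of ketoacidosis not closely related to pump site failure is a removal criterion (sections 2.2 and 6.5), so the message should not be looser than the rule meant to prevent such an episode.

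**Working it through.** The plan gives no figure to reproduce here. The check is a comparison of the texts for a reading above 270 mg/dL.

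| Text | Condition | Ketone test | Level that triggers action | Action |
|---|---|---|---|---|
| Section 2.2, Hypoglycemia and Hyperglycemia | No recent meal | Blood | 1.0 mmol/L or more | No exercise |
| Section 2.2, severe events | None stated | Urine | Any | Emergency contact; study exercise suspended until the diabetes provider advises |
| Section 8.7, Tracking A | During or within 1 hour of exercise | Device-captured ketones | 1.0 mmol/L or more | Labelled diabetic ketoacidosis; exercise suspended |
| Table 3, tip B | Before exercise, meal or not | Blood or urine | Any positive | Vigorous activity restricted |

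**Blood ketones of 1.0 mmol/L or more, no recent meal.** Section 2.2 rules out exercise of any intensity. Tip B restricts one intensity. Its last sentence clears exercise only when ketones are absent, so light exercise is not expressly allowed, but it is not ruled out either. Tip B is looser here, and this is the main conflict.

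**Positive urine test.** Section 2.2 suspends all study exercise. Tip B gives the same advice as for a positive blood test. A urine result also cannot be read against a cut-off in mmol/L of blood. Tip B is looser again, but this part is secondary, because the study mails every participant a blood ketone meter and strips (section 6.1.1, Mailing) and demonstrates them at Visit 2.

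**Blood ketones present but below 1.0 mmol/L.** Section 2.2 does not rule out exercise, while tip B restricts vigorous activity. Tip B is the more cautious text.

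**Recent meal.** Section 2.2 exempts such readings from its blood ketone rule. Tip B asks for a test regardless, which is again more cautious and worth keeping.

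**Is the message checked before it goes out?** The exercise physiologist edits Tool #2 messages and reviews Tool #4 results. No such step is described for Tool #3, whose reports come from the app's cloud. No other wording for tip B appears in the documents.

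**The case against.** The strongest reply is that tip B is not the operative safety rule. The 1.0 mmol/L rule is stated twice in section 2.2. Safe glucose ranges are part of the safety orientation, which the exercise physiologist covers when the app is introduced at Visit 4. Table 3 is titled as an example. The orientation handout (Appendix 22a) is not among the documents, so what participants finally read about ketones cannot be fully judged. This lowers the practical risk. It does not reconcile the texts: the pattern times in Table 3 are plainly illustrative, but tip B is generic wording with no alternative given.

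Monitoring also helps. Staff check the dashboard daily for exercise safety (Tool #2 and section 8.7, Tracking A), and a physician reviews this same pattern every two weeks (Tracking B). These are real but partial safeguards. Tracking A lists its daily signals for the first two weeks, the Tool #2 text does not say that automatic suspension continues beyond them, and no review is described as checking the report's wording.

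On urine, one can fairly say that the severe-event definition is itself too broad, since a trace result would call for emergency contact. That is a reason to give the urine part less weight. It leaves the blood ketone conflict untouched.

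A reader might also infer that tip B tells people with ketones that light exercise is safe. It does not: its last sentence clears exercise only without ketones. The supportable claim is that the case is under-restricted.

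**Conclusion.** Tip B is wrong as written: a participant-facing safety message that is looser than the protocol's own rule at blood ketones of 1.0 mmol/L or more and, secondarily, on a positive urine test. Severity is minor. The conclusion rests on the wording alone and assumes that the message is sent as Table 3 shows it.

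The documents give neither a distribution of glucose at the start of exercise nor a rate of raised ketones, so no number of affected sessions can be supported. The event is probably rare. A reader might infer that harm is likely, or that Outcome 1-3-2 is affected. Neither follows: the partial safeguards stand, and the outcome counts patterns by their definitions, not by the tips. Nor is tip B looser throughout, given its extra caution below 1.0 mmol/L and after meals.

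**What to change.** Reword tip B so that it meets section 2.2 and keeps its present cautions:

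*If your glucose is above 270 mg/dL before exercise, test your blood ketones with the study meter. If ketones are 1.0 mmol/L or higher, or if you used a urine test and it is positive, do not exercise, and contact your diabetes provider or the emergency contact in your safety instructions before exercising again. If blood ketones are present but below 1.0 mmol/L, avoid vigorous activity.*

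The existing closing sentence can stay. The urine clause follows from the severe-event definition in section 2.2; if the sponsor thinks that definition too broad, it should be changed there first and the message aligned to it.

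The cost is one IRB wording amendment. The blood meter and strips are already supplied. The Table 3 pattern definitions, the code that detects them, the count for Outcome 1-3-2 and all analyses stay unchanged.

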### 3.2 Hypothesis

### **PRIMARY**

*Hypothesis 1-1*: The mobile intervention will meet standards of feasibility.

Hypothesis 1-2: The mobile intervention will generate positive user feedback and suggested refinements.

Hypothesis 1-3-1: The data will verify that a prior-constructed machine-learning algorithm that predicted exercise adherence in a prior dataset will continue to do so with acceptable accuracy (receiver-operator characteristic AUC .80, or precision-recall AUC .80 if <20% of days are lapses).

Hypothesis 1-3-2: The data will verify that prior detected patterns in blood glucose safety hazards will continue to appear with expected frequency (≥1 of the above patterns occurring in ≥80% of person-weeks).

Hypothesis 1-3-3: The data will verify that small or greater (d≥0.1) changes in blood glucose resulting from exercise are detectable by a Bayesian model.

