The mathematical basis of the R-code is our Bayesian time series model. Briefly, it compares CGM metrics over each 1-4 week period against a counterfactual predicted based upon the CGM during the 1-4 weeks before the period and the covariates over the 1-4 week period. The full formalism and an example of this analysis is available in our manuscript¹00. The advantage over linear modeling frameworks is the flexibility to evaluate the intervention's effect strength at all points in the intervention period. If p-values do not reach significance (α=.05) then the next version of the app will extend the length of the testing window before providing feedback, though even 1 week of CGM data at minimal adherence (70%) yields k=1,411 observations resulting in 96% power to detect a small effect size (d≥0.10) at α=.05. The maximum window of 4 weeks was chosen as a typical minimal frequency of health coaching sessions for long-term maintenance of lifestyle change¹01.

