If needed, separate models for subgroups can be established in the subsequent beta version of the app. Third, model-generated messages will be validated against the human-edited messages that are released to participants during the study (c.f. Sect 6.1.1, tool #2). Models are evaluated by the number of lapses required to train person-level models to reach acceptable accuracy (receiver-operator characteristic AUC .80, or precision-recall AUC .80 if <20% of days are lapses), thus estimating a "learning window" before users can expect adaptive feedback. Third,

**Hypothesis 1-3-2. Detect Exercise Safety Hazards.** Tabulate the occurrence of the common safety hazards (Table 3) and report them by frequency statistics.

**Hypothesis 1-3-3. Assessing Exercise Glycemic Response.** The mathematical basis of the R-code is our Bayesian time series model. Briefly, it compares CGM metrics over each 1-4 week period against a counterfactual predicted based upon the CGM during the 1-4 weeks before the period and the covariates over the 1-4 week period. The full formalism and an example of this analysis is available in our manuscript. The advantage over linear modeling frameworks is the flexibility to evaluate the intervention's effect strength at all points in the intervention period. If p-values do not reach significance ( $\alpha$ =.05) then the next version of the app will extend the length of the testing window before providing feedback, though even 1 week of CGM data at minimal adherence (70%) yields k=1,411 observations resulting in 96% power to detect a small effect size (d≥0.10) at  $\alpha$ =.05. The maximum window of 4 weeks was chosen as a typical minimal frequency of health coaching sessions for long-term maintenance of lifestyle change.

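### Tool #4 and Hypothesis 1-3-3 predict the counterfactual from the exercise done in the evaluated window, so part or all of the exercise effect can be removed

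*Combined protocol and SAP*

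**What the plan says.** Section 3.2 sets Hypothesis 1-3-3 under Primary Objective 3: the data should verify that "small or greater (d≥0.1) changes in blood glucose resulting from exercise are detectable by a Bayesian model". Section 6.1.1 (Visit 4) describes Tool #4, which uses the same model, as "Health outcome feedback regarding the causal impact of exercise upon blood glucose". Its inputs are CGM metrics and "covariates (insulin-on-board, carbohydrates self-reported into insulin device, exercise metrics including video selected and Fitbit minutes / heart rate / distance / calories", followed by sleep and activity below exercise intensity.

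The next paragraph compares CGM metrics in each evaluated window, one to four weeks long, "against a counterfactual predicted based upon the CGM during the 1-4 weeks before the period and the covariates over the 1-4 week period". Section 7.2, Hypothesis 1-3-3, repeats this: the prediction uses "the CGM during the 1-4 weeks before the period and the covariates over the 1-4 week period". Both places say that one week of CGM at 70% adherence "yields k=1,411 observations resulting in 96% power to detect a small effect size (d≥0.10) at α=.05". If significance is not reached, the next app version is to lengthen the testing window.

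Nothing in the text sets exercise metrics to a reference value when predicting, or restricts covariates to variables that exercise cannot change. Details are deferred to a cited manuscript and to the Appendix 9b code, which are not part of the text reviewed.

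**The concern.** The study has one group, so the modelled counterfactual is the only comparator for the effect of exercise on glucose. To isolate that effect, the prediction must represent glucose without the exercise in question. A prediction that is given the minutes, heart rate, distance, calories and video actually recorded represents glucose with that exercise, to the extent that the model has learned the relation from the prior window.

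Insulin-on-board and carbohydrates raise a related issue. Section 2.2 (Hypoglycemia) describes insulin adjustment and carbohydrate intake around exercise, so their in-window values are partly consequences of exercise. Conditioning on them changes the quantity estimated from a total to a direct effect, and the plan does not say which is wanted.

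Two things are at stake. The exercise physiologist relays positive, neutral or negative effects to participants, and an attenuated estimate could be relayed as neutral. A non-significant result would also prompt a longer window, which does not cure this problem.

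**Working it through.** **1. The plan's own figure.** Inputs from Section 6.1.1: one reading per 5 minutes (288 per day), 7 days, 70% adherence, d = 0.10, α = .05.

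- k = 7 × 288 × 0.70 = 1,411.2 (stated 1,411).
- Two-sided one-sample z test with independent readings: d√k = 0.10 × √1,411 = 3.756; power = Φ(3.756 − 1.960) = 96.4% (stated 96%).

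Both figures reproduce, on the condition that all of d = 0.10 remains after adjustment.

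**2. Power when only a share f survives.** Power = Φ(f × 3.756 − 1.960) + Φ(−f × 3.756 − 1.960).

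| f | f × 3.756 | Power |
|---|---|---|
| 1 | 3.756 | 96% |
| 0.75 | 2.817 | 80% |
| 0.50 | 1.878 | 47% |
| 0.25 | 0.939 | 16% |
| 0 | 0 | 5% |

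**3. How the share depends on the prior window.** A linear regression stands in for the Bayesian model: fit it on the prior window, predict the evaluated window from that window's own covariates, and average observed minus predicted. Assumptions: 1,411 independent readings per window; exercise in 30% of evaluated readings; effect 0.10 SD against no exercise; 40% of it acting through insulin and carbohydrate, in the same direction.

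| Exercise share, prior → evaluated | True change | No covariates | Exercise metrics only | Insulin/carbohydrate only | Both |
|---|---|---|---|---|---|
| 0% → 30% | 0.100 | 0.099 | 0.095 | 0.058 | 0.061 |
| 10% → 30% | 0.067 | 0.063 | −0.005 | 0.039 | 0.001 |
| 30% → 30% | 0 | 0.000 | 0.004 | −0.003 | 0.003 |

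In the first row the exercise metric is constant at zero beforehand, so its slope cannot be learned and almost nothing is lost to it. In the second row the slope is learned and the whole change disappears. In the third row there is no change to detect with any covariate set, because the reference already contains exercise. That is a matter of which prior weeks are chosen, not of covariates.

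**4. Sedentary prior window with varying Fitbit activity.** Fitbit is worn from Visit 2 (Table 1), so everyday activity is recorded before the app starts. Let g be the glucose slope for everyday activity relative to the slope for exercise, and m the share of the effect acting through insulin and carbohydrate. Then:

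share left = (1 − m)(1 − g).

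With m = 0, the share is 100% at g = 0, 50% at g = 0.5 and 0% at g = 1. With m = 0.4 and g = 0.5 it is 0.6 × 0.5 = 30%. Simulation agreed with the formula.

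**5. A daily-level illustration.** Assumptions: 14 days per window, mean active minutes rising from 10 (SD 8) to 32 per day, slope −0.02 SD per minute. The true effect is −0.431 SD. The estimate is −0.435 without minutes as a covariate and +0.006 with them. If the prior-window slope is half or zero times the exercise slope, the formula gives 0.5 × −0.431 = −0.22 or −0.43; simulation gave −0.19 and −0.42.

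**The case against.** The strongest reply is that the two sections give only a summary. The list in Tool #4 is what the app draws, not a regression equation, and the exercise metrics may serve only to label exercise type in the feedback. This cannot be checked without Appendix 9b. It does not rescue the wording: the metrics are called covariates, and the counterfactual is predicted from the covariates in the period. If the code does otherwise, the text needs correcting; if not, the code does.

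A reader might infer that the effect is always subtracted in full. The documents do not support that. Section 5.3 admits people with fewer than one exercise session a week and the app starts at Visit 4, so in the first window no video slope can be learned. The daily illustration assumes 32 minutes a day (224 a week), against a 150-minute weekly target and a pilot median of 64 a week (Section 1.2.1). It shows the mechanism, not the expected size.

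A reader might also infer that adjusting for insulin and carbohydrate always biases towards no effect. That does not follow. Where exercise lowers glucose, compensating intake or insulin changes can oppose the direct effect. For example, with an assumed direct effect of −0.10 and compensation of +0.04, the total is −0.06, and adjustment returns the larger −0.10. Section 1.1 says glucose can move either way. These variables can also be confounders, for instance when a provider changes insulin in the same weeks, so leaving them out has a price.

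Finally, this is one of three hypotheses under one primary objective of an alpha-version feasibility study, and Section 7.2.3 says that treatment effect is not being evaluated. That limits the consequence. It does not make the estimate match the effect that the hypothesis names.

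**Conclusion.** The concern holds in a limited form. As written, exercise metrics from the evaluated window help to build the comparator for exercise, and observed minus predicted removes whatever part of the effect was learned beforehand. The loss runs from almost none (sedentary prior window, everyday activity unrelated to glucose) to essentially all (exercise rising from a non-zero level, or everyday activity with the same slope as exercise). If windows are one week long and each is compared with the week before, three of the four intervention weeks have a reference week that falls inside the intervention.

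The 96% power is correct arithmetic for a fully surviving effect only. The powers in step 2 keep the plan's treatment of 5-minute readings as independent, so they show the relative cost of attenuation and are not realistic power in themselves. The simulated sizes rest on linear slopes, no shrinkage and the assumed exercise and mediation shares; shrinkage priors would leave more of the effect. For insulin and carbohydrate, the supported conclusion is that the estimand is undeclared; no general direction of bias is shown.

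**What to change.** - In Section 6.1.1 (Tool #4), Section 7.2 (Hypothesis 1-3-3) and the Appendix 9b code, exclude all exercise metrics from the regressors that build the counterfactual: video selected, Fitbit minutes, heart rate, distance, calories and sub-exercise activity. Alternatively, hold them at their prior-window or no-exercise value when predicting. Use the recorded values only to describe exercise dose and type.
- State the estimand: total or direct effect, and relative to prior behaviour or to no exercise.
- Report each window with and without in-window insulin-on-board and carbohydrates, labelled as direct and total effect respectively.
- State that the 96% power assumes that the full d = 0.10 survives adjustment.

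The cost is a revised covariate list, a sentence or two in each section and one extra model run per window. The total-effect estimate will be noisier, and insulin or diet changes that coincide with the window will be attributed to exercise. Reporting both versions makes that visible.
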